6.3. Flow Chart PE arm

Table 3: Study flow chart PE arm, Screening to End of Study

Visit Number	1	2	3	4	5	6	7	8	9	10	11	
Type of visit	Screening	Treat- ment	Assessments								FU/End of study	
Day		1-5	6	8	11	15	22	29	64	90	180	
Assessment /Time window			0	0	±2d	±2 d	±3 d	±3 d	±7d	±7d	±14d	
Informed Consent	X	See table 4										
Demographics	X											
Medical/surgical history, incl transplantation and previous AMRs	X											
Record historical creatinine values	X											
Record number of pregnancies (if applicable)	X											
Inclusion/exclusion criteria	X											
Randomization	X											
Physical examination	X										X	
Height and weight	X											
Blood pressure and pulse rate	X			X	X	X	X	X	X	X	X	X
Respiratory frequency	X											
Body temperature	X			X	X	X	X	X	X	X	X	X
PCR test for SARS-CoV-2 virus	X											
ECG	X											X
Pregnancy test (serum)	X											X
Pregnancy test (serum) Austria	X								X	X	X	X
Safety laboratory tests (incl creatinine for eGFR)	X			X	X	X	X	X	X	X	X	X
Urine sample for measurement of albumin/creatinine ratio	X			X	X	X	X	X	X	X	X	X
ADA (IgE)	X ^a											
DSA, incl HLA antibodies and functionality (if applicable, taken before PE)	X ^b			X	X	X	X	X	X	X	X	X

Table 3: Study flow chart PE arm, Screening to End of Study

Visit Number	1	2	3	4	5	6	7	8	9	10	11
Type of visit	Screening	Treat- ment	Assessments								FU/End of study
Day		1-5	6	8	11	15	22	29	64	90	180
Assessment /Time window			0	0	±2d	±2 d	±3 d	±3 d	±7d	±7d	±14d
PK sampling			X	X	X	X					
PD sampling (if applicable, taken before PE)			X ^d	X ^{d,e}	X ^{d,e}	X	X	X	X	X	X
ADA(IgG)				X	X	X	X	X	X	X	X
Kidney biopsy	X ^c							X ^c			X ^c
Methylprednisolone /Prednisolone			Will be given according to treatment schedule (section 5.3) and continue as long as prescribed by investigator								
Antibiotic prophylaxis			Treatment will continue until IgG levels return to acceptable values, as judged by the investigator								
High dose IVIg			High dose IVIg will be given after last PE session. Dose may be given over two days								
Rituximab				Will be given 5 days after completed high dose IVIg							
Concomitant medication and other treatment	Throughout the study										
Adverse events	Throughout the study										

^{a)} Sample will be taken pre-dose but no need to wait for result before start of treatment

^{b)} One DSA sample will be sent to local lab for evaluation of inclusion and one DSA sample will be collected for analysis at Hansa Biopharma

^{c)} One piece of tissue will be sent to local pathology lab and one piece of tissue will be sent for analysis at [REDACTED]

If kidney biopsy is performed prior to screening, a piece of tissue cannot be sent for [REDACTED] analysis unless site stores tissue in mRNA later as standard of care. Then the tissue may be sent for [REDACTED] analysis after informed consent is signed.

^{d)} If high dose IVIG is given, the PD sample must be taken prior to IVIg

^{e)} If high dose IVIg is completed and there is no scheduled PD sample at the latest the following day, an additional PD sample will be taken

Table 4: Study flow chart PE arm, visit 2, treatment

Visit Number	2									
Time	Pre-dose	Treat-ment	30 min	1 h	2 h	6 h	24 h	48 h	72 h	96 h
Assessment /Time window			±10 min	±10 min	±15 min	±30 min	±2h	±2h	±6h	±6h
Blood pressure and pulse rate	X				X	X	X	X	X	X
Respiratory frequency	X						X	X	X	X
Body temperature	X						X	X	X	X
Safety laboratory tests (incl creatinine)							X	X	X	X
Methylprednisolone/prednisolone ^a	X						X	X	X	X
Antibiotic prophylaxis	X		Treatment will continue until IgG levels return to acceptable values, as judged by the investigator							
DSA, incl HLA antibodies and functionality (if applicable, taken before PE)	X				X	X	X	X	X	X
PK sampling	X				X	X	X	X	X	X
PD sampling functionality (if applicable, taken before PE)	X				X	X	X	X	X	X
ADA (IgG)	X						X			
P-creatinine (for calculation of eGFR)	X									
Urine sample for measurement of albumin/creatinine ratio	X						X	X	X	X
PE		X								
Concomitant medication and other treatment	Throughout the visit									
Adverse events	Throughout the visit									

^{a)} Methylprednisolone/prednisolone will be given according to the treatment schedule in Section 5.3

7. STUDY ASSESSMENTS

When different assessments are scheduled at the same time according to the flow chart, samples for DSA, PK and PD should be prioritized to be taken at the exact time point. Exact time points must be entered into the eCRF. All sampling, shipping and analysing of laboratory samples will be detailed in the laboratory manual.

7.1. Assessments related to endpoints

Samples for DSAs and pharmacodynamics (PD) will be collected at multiple time points as indicated in the study flowcharts ([Table 1](#), [Table 2](#), [Table 3](#) and [Table 4](#)). DSAs will be identified by each site using HLA profile data from the donor and the patient together with Single Antigen Bead (SAB) analysis data obtained at baseline.

7.1.1. Determination of donor specific antibodies

Samples for determination of DSAs and HLA-antibodies will be analyzed in a single antigen bead assay (HLA-SAB) as well as in functional assay e.g. C1q or C3d assay. These assays allow determination of the mean fluorescence intensity (MFI) of antibodies in subject serum reacting to an array of individual HLA immobilized to beads. Analyses of HLA antibodies, including DSA, will be performed centrally. The date and actual time of collection of each sample will be recorded in the eCRF. DSAs for each patient will be identified by respective site. DSAs collected in standard of care at other timepoints will also be recorded in the eCRF

DSA taken at screening will also be analysed at the local lab at each site, in addition to centrally, for determination of presence of DSA(s) for inclusion.

7.1.2. Pharmacodynamics

Samples for the determination of IgG levels in serum (PD) qualitative analysis of IgG-fragments will be taken at the times presented in the study flow chart ([Table 1](#), [Table 2](#), [Table 3](#) and [Table 4](#)). The date and actual time of collection of each sample will be recorded in the eCRF. Samples for determination of IgG levels in serum will be analysed with a validated electrochemiluminescence based immunoassays using the MSD (Meso Scale Diagnostic) technology. Full details of the analytical method used, and the analysis results will be detailed in a separate bioanalytical report. IgG-fragments will be analysed by SDS-PAGE and Western blot, using antibodies directed to human IgG fragments.

7.1.3. Kidney function as evaluated by eGFR, P-creatinine and albumin/creatinine ratio in urine

Evaluation of kidney function based on P-creatinine analysis and calculation of filtration rate (eGFR) using MDRD GFR Equation. Calculation of eGFR will be done directly in the eCRF. Albumin/creatinine ratio in urine will be performed at the time points indicated in the study flowcharts ([Table 1](#), [Table 2](#), [Table 3](#) and [Table 4](#)). Creatinine values collected in standard of care at other timepoints will also be recorded in the eCRF.

7.1.4. Kidney biopsy

Kidney biopsies collected at screening or within 5 days prior to screening, on day 29 and day 180 will be assessed according to the Banff 2017 (Haas et al. 2018) criteria, by a local pathologist. In addition, a piece of tissue from the kidney biopsy will be evaluated on the basis of microarray mRNA measurement using the [REDACTED] a central diagnostic system. If the initial kidney biopsy is performed prior to screening and signed informed consent, mRNA levels will be evaluated on day 29 and day 180. If kidney biopsies are performed at any other time points, if judged necessary by the PI, reports from those will be collected and documented in the eCRF.

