5.4. Blinding

This is an open-label study. Due to the nature of the control treatment, blinding of the control treatment is not feasible.

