- ^{c)} One piece of tissue will be sent to local pathology lab and one piece of tissue will be sent for analysis at [REDACTED]. If kidney biopsy is performed prior to screening, a piece of tissue cannot be sent for [REDACTED] unless site stores tissue in mRNA later as standard of care. Then the tissue may be sent for [REDACTED] analysis after informed consent is signed.
- ^{d)} Rituximab will be given 5 days after completed high dose of IVIg

Table 2: Study flow chart imlifidase arm, visit 2, treatment

Visit Number	2									
Time	Pre-dose	Treat-ment	30 min	1 h	2 h	6 h	24 h	48 h	72 h	96 h
Assessment /Time window			±10 min	±10 min	±15 min	±30 min	±2h	±2h	±6h	±6h
Blood pressure and pulse rate	X				X	X	X	X	X	X
Respiratory frequency	X						X	X	X	X
Body temperature	X						X	X	X	X
Safety laboratory tests (incl creatinine)							X	X	X	X
Methylprednisolone/prednisolone ^a	X						X	X	X	X
Antihistamine	X									
Antibiotic prophylaxis	X		Treatment will continue until IgG levels return to acceptable values, as judged by the investigator							
DSA, incl HLA antibodies and functionality	X				X	X	X	X	X ^b	X
PK sampling	X		X	X	X	X	X	X	X ^b	X
PD sampling	X				X	X	X	X	X ^b	X
ADA (IgG)	X						X			
P-creatinine (for calculation of eGFR)	X									
Urine sample for measurement of albumin/creatinine ratio	X						X	X	X	X
Imlifidase infusion		X								
High dose IVIg									X ^c	
Concomitant medication and other treatment	Throughout the visit									
Adverse events	Throughout the visit									

^{a)} Methylprednisolone/prednisolone will be given according to the treatment schedule in section 5.3

^{b)} Samples should be taken prior to start of high dose IVIg is given

^{c)} May be given over two days

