2.3 Blinding

The study is an open-label study. The study is fully unblinded.

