4.6.2 Secondary efficacy analyses

DSA levels up to 180 days after treatment

DSAs will be measured using SAB-HLA assay and a functional assay e.g. C1q or C3d assay. A summary table for the C1q assay will be generated for the sum of MFI levels for DSAs from step 1 for primary endpoint (see Section 4.6.1) by treatment and time point. MFI levels will be listed per patient and time point. Spaghetti plots will show the DSA level versus time for each patient. A mean plot by treatment and time point will be presented.

A list with all DSA by patient and time point will be presented.

HLA-antibodies levels up to 180 days after treatment

Patient listings of MFI values for all HLAs will be presented.

Kidney function change from baseline

The kidney function will be evaluated by the parameters eGFR, P-creatinine and albumin/creatinine ratio in urine. The laboratory parameters will be summarised as part of the safety data tabulation.

The eGFR will be calculated as a part of ADaM programming, using the Modification of Diet in Renal Disease Study (MDRD) equation (2):

$$\text{eGFR (mL/min/1.73 m}^2\text{)} = 175 \times (\text{Cr})^{-1.154} \times (\text{Age})^{-0.203} \times (0.742 \text{ if female}) \times (1.212 \text{ if African American}),$$

where Cr stands for creatinine value and Age are measured in years from birth to screening visit. This formula assumes that Cr is given in the mg/dL unit.

Proportion of patients with graft loss at day 180

The number of patients with graft loss at day 180 will be handled as a binary variable. Graft loss is defined as permanent return to dialysis for at least 6 weeks, re-transplantation, or transplantectomy. The endpoint is a success if the patients have absence of graft loss at day 180. The proportion of patients, which satisfy the success criterium, will be summarized by treatment and listed by patient. The FAS set will be applied.

Signs of transplant glomerulopathy 180 days post treatment

Possible transplant glomerulopathy 180 days post treatment will be handled as a binary variable. The endpoint is a success if the patients have no possible transplant glomerulopathy 180 days post treatment. The proportion of patients, which satisfy the success criterium, will be tabulated by treatment. A list will also be created by patient. The FAS set will be applied.

Change from baseline in histopathology per Banff Criteria at 29 and 180 days

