Kidney biopsies will be assessed according to the Banff (2017 or later version) criteria pre-dose and at day 29 and 180. The biopsy data are measured as scores. The scores will be presented by time point in

a summary table. The change from baseline will be summarised by treatment, Banff lesion score and time point.

The overall interpretations for the biopsies will be presented in a summary table by time point. Shift tables will also be presented for overall interpretation from the biopsies. The possible categories for the overall interpretation are: Active AMR, Chronic Active AMR, CMR, Borderline CMR and No rejection. Possible combinations for the overall interpretation are: Active AMR + CMR, Active AMR + Borderline CMR, Chronic Active AMR + CMR and Chronic Active AMR + Borderline CMR.

A list will also be presented by patient where the scores and diagnosis are presented.

Change from baseline in mRNA levels in kidney biopsies evaluated by [REDACTED] at 29 and 180 days from baseline

[REDACTED] data will be presented in a summary table and in a list for day 29 and day 180. The [REDACTED] data is also given as score. The change from baseline will also be presented in a summary table. If baseline data is not available for [REDACTED], only the values on day 29 and 180 will be presented.

Number of sessions with PE for 180 days

The number of PE and immunoabsorption (IA) sessions within 180 days will be summarized by treatment and listed by patient. In addition, the number of PE and IA sessions after start of IVIg administration and up to 180 days after start of study treatment will be summarized by treatment. The FAS set will be applied.

Total serum IgG over time

The FAS set will be applied when analysing total serum IgG.

The IgG levels in serum will be analyzed centrally by a validated ECL based immunoassay using the Meso Scale Diagnostic technology. The total serum IgG levels will be summarized by time point. Total serum IgG levels will also be presented by mean and spaghetti plots. Finally, data will be listed by patient.

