In addition, the reduction of total serum IgG levels will be analyzed as a binary endpoint. The binary endpoint is defined as a success, if the minimum IgG value at any time point during the 5 days following the start of treatment is less than 5% of baseline for the patient. The proportion of patients, which satisfy the success criterium, will be presented in a summary table by treatment. The difference in proportion between the two treatments will be presented with a 95% CI in a summary table. The 95% CI for the difference between the two treatments will be based on exact Confidence Limits. In addition, the proportion of patients which satisfy the success criterium will be presented by treatment and time point.

The composition of IgG-fragments will be analyzed centrally using SDS-PAGE. Each sample will be assigned a score depending on the observed composition of fragments as follows:

- 0=no intact IgG, scIgG or F(ab')₂
- 1=only F(ab')₂
- 2=mix of scIgG and F(ab')₂
- 3=only scIgG
- 4=mix of intact IgG and scIgG
- 5=only intact IgG

SDS-PAGE scores will be summarized by time point.

Presence of intact IgG on SDS-PAGE until start of IVIg treatment

The endpoint is a success for a patient if no detectable intact IgG is found by the SDS-PAGE assay for at least one time point between the start of study medication (imlifidase) treatment and start of administration of IVIg. No detectable intact IgG is defined as SDS-PAGE scores 0, 1, 2 or 3. The

proportion of patients, who reached the success criterium, will be summarized in a table using the PKS set.

Number of patients with resolution of AMR at day 180

The number of patients with resolution of AMR at day 180 will be handled as a binary variable. Resolution is defined as “Active AMR” or “Chronic active AMR” not being selected from the biopsy protocol.

The endpoint is a success if the patients have resolution of AMR at day 180. The proportion of patients, which satisfy the success criterium, will be tabulated by treatment. A list will be created by patient. The FAS set will be applied.

Patient survival at day 180

The patient survival on day 180 will be handled as a binary variable.

The endpoint is a success if the patients have survived on day 180. The proportion of patients, which satisfy the success criterium, will be summarized and listed by patient. The FAS set will be applied.

Pharmacokinetic

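### The day 29 and day 180 biopsies are scored locally with nothing to keep the treatment arm from the reader; masking that reader would cheaply reduce a bias risk in the secondary histology endpoints.

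*Protocol*

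**What the plan says.** Protocol 7.1.4 has the screening, day 29 and day 180 biopsies assessed under Banff 2017 "by a local pathologist". The footnote to the flow chart in Protocol 6.2 matches this: "One piece of tissue will be sent to local pathology lab". A second piece of each biopsy goes for a central mRNA analysis. The documents describe no central, second or coded reading of the Banff histology.

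On blinding, SAP 2.3 states: "The study is fully unblinded". Protocol 5.4 gives the reason: "Due to the nature of the control treatment, blinding of the control treatment is not feasible".

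SAP 4.6.2 builds these secondary endpoints on histology:

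- AMR resolution at day 180 is met when the two AMR categories are recorded as "not being selected from the biopsy protocol".
- For Banff scores, "The change from baseline will be summarised by treatment, Banff lesion score and time point". Shift tables of the overall interpretation are also planned.
- For transplant glomerulopathy, "The endpoint is a success if the patients have no possible transplant glomerulopathy 180 days post treatment". No reader or criterion is named.

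**The concern.** PE cannot be disguised from the patient or the treating team. That does not prevent a slide from being read without knowledge of the arm. The plan gives a reason for the first and says nothing about the second.

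Lesion grading, and the choice between categories such as borderline cellular rejection, chronic active AMR and no rejection, involve judgement. A reader who knows the arm may settle borderline cases in a consistent direction. The results are presented by treatment, so a shift of that kind would look like a treatment difference.

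This matters because Protocol 1.3 expects quicker DSA removal to spare the graft. The primary endpoint measures antibody level only, so evidence on graft injury has to come from elsewhere, and the local histology is a substantial part of it.

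**Working it through.** **1. What the blinding statements cover.** Protocol 5.4 is about giving the control treatment. SAP 2.3 is a general statement that nothing is blinded. Neither mentions the pathologist, and no other section describes withholding the arm from that reader.

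**2. Which reads are exposed.** Meeting the Banff criteria is an inclusion criterion (Protocol 4.2, criterion 5), and randomisation is the last step listed for the screening visit (Protocol 6.1.1). The screening read should therefore normally come before allocation. The exposed reads are those at day 29 and day 180.

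**3. Which endpoints are exposed.**

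- AMR resolution at day 180: exposed, because it is decided by the category this reader selects.
- Banff change and shift at days 29 and 180: exposed.
- Transplant glomerulopathy at day 180: exposed by inference, since a day 180 biopsy read is the natural source, but neither document says so.
- Primary DSA endpoint: not exposed. Protocol 7.1.1 says "Analyses of HLA antibodies, including DSA, will be performed centrally".
- mRNA results: not exposed, because they come from the central system.
- Graft loss: not exposed, because SAP 4.6.2 defines it by return to dialysis, re-transplantation or transplantectomy.

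**4. The plan's own figure.** The plan gives no precision figure for the histology endpoints. Its only one is a 95% CI about 8 points wide for DSA reduction (Protocol 12.4, SAP 2.2). The root mean square of the two quoted SDs is √((6² + 4²)/2) = 5.10. The full width is then 2 × 2.048 × 5.10 × √(1/20 + 1/10) = 8.1 points using t with 28 df, or 7.7 using z. The figure reproduces, but it has no bearing on the biopsy endpoints.

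**5. What one call is worth.** With the planned 20 and 10 patients, one changed call moves the day 180 proportion by 1/10 = 10 points in the PE arm or 1/20 = 5 points in the imlifidase arm. Missing biopsies would make the steps larger.

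**6. Illustration on assumed rates.** None of these rates is in the documents. Let true resolution be p in both arms, and let an aware reader call a share f of unresolved imlifidase biopsies resolved. The spurious difference is (1 − p) × f.

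- p = 0.5, f = 0.1: 0.5 × 0.1 = 5 points (1 of 20 patients).
- p = 0.5, f = 0.2: 0.5 × 0.2 = 10 points (2 of 20).
- For p from 0.3 to 0.7 and f from 0.05 to 0.3, the range runs from 0.3 × 0.05 = 1.5 points to 0.7 × 0.3 = 21 points.

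The approximate 95% half-width for the difference is 1.96 × √(p(1 − p)(1/20 + 1/10)). This gives 35 points at p = 0.3 or 0.7 and 38 points at p = 0.5. Bias of the illustrated size could not be detected from the data afterwards, so it has to be prevented by procedure.

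**The case against.** The exposure is inferred. No passage says the pathologist is told the arm, and a local reader is not necessarily an informed one. Protocol 7 leaves sampling, shipping and analysis details to a laboratory manual that is not among the documents, and the manual may already deal with this. That stands. The gap is that nothing in the protocol or SAP prevents awareness, not that awareness is shown.

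The endpoints are secondary, no hypothesis is tested, and the SAP plans no confidence interval for a treatment difference in any of them. With half-widths of 35 to 38 points, they could not support a firm comparison even if perfectly masked. This limits the importance of the point but does not remove it, because a descriptive proportion presented by arm can still be biased.

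The 10-point and 5-point steps follow from the arm sizes and would apply to any binary endpoint in this trial. That is also correct. They show sensitivity to one call, not the amount of bias.

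The change is not free. Protocol 13.1 requires an amendment with approvals where applicable. The SAP introduction lists five country-specific protocols, and Protocol 3.3 gives about 14 sites. On the timeline in Protocol 3.2 (start in Q1 2019, 35 months of recruitment), the US version of 17 November 2021 falls near the end of enrolment. A late change would mix reads made with and without masking.

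Masking can also go too far. Protocol 3.1 uses Banff 2017 criteria that include presence of DSA, so stripping DSA status from the request would remove information the diagnosis needs.

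**Conclusion.** The point holds for the day 29 and day 180 reads, as a cheap improvement to secondary, descriptive histology endpoints. AMR resolution and Banff change and shift are directly open to assessor bias. Glomerulopathy is open only if, as seems likely, it is judged from the same local read.

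The amount of bias is unknown. The firm figure is the value of one call: 10 points in the PE arm or 5 in the imlifidase arm, assuming all 10 and 20 patients contribute. The 1.5 to 21 point range rests wholly on assumed rates.

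A reader might infer more than the documents support:

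- **That the pathologists know the arm, or that the histology results are biased.** Neither document says so.
- **That the main result is compromised.** The primary endpoint is a centrally analysed antibody level and does not use the biopsy read.
- **That no independent graft evidence remains.** The central mRNA results and graft loss do not depend on this reader.
- **That baseline scores are affected too.** The screening read should normally precede randomisation.

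**What to change.** In Protocol 7.1.4 and the laboratory manual, for the day 29 and day 180 biopsies:

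- The biopsy request and the study scoring form omit the treatment arm and treatment details. They keep the subject number, the visit and the DSA status needed for the Banff diagnosis.
- The local pathologist records the Banff scores and the overall interpretation while unaware of the arm.
- The study does not disclose the arm to that reader until the subject's day 180 read is recorded. Disclosure straight after the day 29 read would undo the masking at the visit that defines AMR resolution.
- Any unmasking, including for clinical need, is recorded, and so are reads made before the change.

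If the laboratory manual already requires this, a sentence in 7.1.4 saying so is enough.

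Cost: the same reader, slides and biopsies are used, and no endpoint, sample size or analysis changes. The documents give no cost figure, so calling it cheap is a judgement. The drawbacks are an amendment across the country versions, imperfect masking where the reader works in the treating hospital and may see clinical records, and reads already made that stay unprotected. The change does not address variation between local readers.
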